Estimates from the literature were used to calculate the sample size needed for this study for the outcomes of changes from month 0 to month 5 in our primary outcome, heart failure quality-of-life. We assumed that the standard deviations (SD) seen in the current study would be similar to that in a similar study conducted in an urban setting in the United States.¹³ Sample size calculation were based assuming 80% power for a two-sided test at alpha of 0.05, and SD of 20.0. With the outcome of change in heart failure quality of life score from baseline to 5 months, considering as a minimum clinical difference of 10 points in the heart failure quality of life score, the sample size

needed was 63 individuals in each arm. We assumed a retention in the current study of 80%, thus the sample size needed at recruitment was at least 158 (n=79 in each arm)

8) Framework

The superiority hypothesis testing framework will be used, testing whether exposure to the intervention results in better outcomes than exposure to the control standard of care. Comparisons will be presented as differences between arms in changes in outcomes from baseline to 1 month to capture changes in acute heart failure symptoms and 30-day readmission; and from baseline to 5 months of follow-up to capture longer term and potentially sustained benefits.

9) Statistical interim analyses and stopping guidance

- a. Information in interim analyses specifying what interim analyses will be carried out and listing time points
 - i. None planned
- b. Any planned adjustment of the significance level due to interim analysis
 - i. No
- c. Details of guidelines for stopping the trial early
 - i. None

10) Timing of final analyses

Final analyses will begin in Fall 2021 upon completion of all field data collection in Fall 2020 and completion of all medical record data collection (Summer 2021).

11) Timing of outcome assessments

Research staff administered full surveys to both arms at baseline, 1 month, and 5 months. Additional brief surveys were collected at months 2 and 3. Medical record data were collected continuously in both arms from 3 months prior to baseline until 9 months after baseline.

Section 4: Statistical Principles

12) Level of statistical significance

95% confidence intervals and exact p-values (or $p<0.001$) will be reported.

13) Description and rationale for any adjustment for multiplicity and, if so, detailing how the type I error is to be controlled.

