- i. Hospitalization and Emergency Department use: As a secondary Aim 1 outcome, self-reported data as well as abstracted medical record data on hospital readmission and Emergency Department use were collected. From the data we will assess the number of times participants were admitted to the hospital from baseline to 1 month and from baseline to five months and the cumulative probability of being hospitalized by study arm. The following outcomes will be reported:

1. Admissions to Zuckerberg San Francisco General Hospital from baseline to 1 month, as determined by medical records. Number of admissions to Zuckerberg San Francisco General Hospital from baseline to 1 month, by study arm, adjusting for baseline values (-3 to 0 months).
2. Admissions to Zuckerberg San Francisco General Hospital from baseline to 5 months, as determined by medical records. Number of admissions to Zuckerberg San Francisco General Hospital from baseline to 5 months, by study arm, adjusting for baseline values (-3 to 0 months).
3. Admissions to any hospital from baseline to 1 month, as determined by ZSFGH medical records and self-report of admission to hospitals other than ZSFGH. Number of admissions to any hospital from baseline to 1 month, by study arm, adjusting for baseline values (-3 to 0 months).
4. Admissions to any hospital from baseline to 5 month, as determined by ZSFGH medical records and self-report of admission to hospitals other

than ZSFGH. Number of admissions to any hospital from baseline to 5 months, by study arm, adjusting for baseline values (-3 to 0 months).

- a. Cumulative probability to be admitted to any hospital from baseline to 5 months by study arm.
- 5. Emergency room utilization at Zuckerberg San Francisco General Hospital from baseline to 1 month, as determined by medical records. Number of admissions to the emergency room at Zuckerberg San Francisco General Hospital from baseline to 1 month, by study arm, adjusting for baseline values (-3 to 0 months).
- 6. Emergency room utilization at Zuckerberg San Francisco General Hospital from baseline to 5 months, as determined by medical records. Number of admissions to the emergency room at Zuckerberg San Francisco General Hospital from baseline to 5 months, by study arm, adjusting for baseline values (-3 to 0 months).

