- 7. Emergency room utilization at any hospital from baseline to 1 month, as determined by ZSFGH medical records and self-report of emergency room utilization at hospitals other than ZSFGH. Number of admissions to any emergency room from baseline to 1 month, by study arm, adjusting for baseline values (-3 to 0 months).
- 8. Emergency room utilization at any hospital from baseline to 5 month, as determined by ZSFGH medical records and self-report of emergency room utilization at hospitals other than ZSFGH. Number of admissions to any emergency room from baseline to 5 months, by study arm, adjusting for baseline values (-3 to 0 months).

ii. Overall health-related quality of life. Self-reported quality of life using the 4-item Healthy Days Core Module of the CDC's Health-Related Quality of Life survey which asks a general assessment of health on a 5-point Likert scale as well as 3 questions quantifying the number of days in the past 30 days participants felt their health was not good.

c. Aim 2 Outcomes. The primary intermediate outcomes are changes between baseline, 1 month and 5 months in food security, diet quality, depressive symptoms, and medication adherence.

- i. Food Security: We measured food security status using the 10-item adult version of the USDA Household Food Security Survey Module (HFSSM) Access Scale (HFIAS). This scale has been validated in Spanish and English in the US and is the reference measure for food security in the US [citations]. The ten-item questionnaire covers domains of worry over, sufficiency of, and quality of food accessed by the participant's household. The scores will be analyzed primarily as a continuous variable using a sum of all responses with a possible range of 0 to 18 in households with children, and 0 to 10 in households without children. Higher scores are indicative of less food security. We will examine the following outcomes:
 - 1. Change in food security scores from baseline to 5 months, by study arm.
 - 2. Change in food security scores from baseline to 1 month, by study arm.

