- ii. Change in dietary patterns: Food consumption was collected using food frequency questionnaire that assess the frequency of intake of 32 food items in the prior month. A change in the consumption (servings/day) of food groups from baseline to one month, and from baseline to five months will be assessed. The food groups to evaluate are food high in: Unsaturated Fat (nuts), Saturated Fat, Sodium, Added sugars, Fruits, Vegetables (fresh), Vegetables (canned), Animal-based Protein, Plants-based Protein, Dairy, and Carbs/Starch.

- iii. Medication adherence. A Single-Item Rating Visual Analogue Scale (range 0-100) for medication adherence will estimate the percentage of medications taken in the past month and is reliable and valid, including in low-literacy populations. A higher value indicates higher adherence. The change in medication adherence (percentage points) from baseline to one month, and from baseline to five months between intervention and control arms will be reported.
- iv. Depressive symptoms. Symptoms corresponding to the Diagnostic and Statistical Manual of Mental Disorders will be measured using the 9-item Patient Health Questionnaire (PHQ-9), a reliable and valid measure of symptom severity. The PHQ-9 score ranges from 0 to 27, with higher scores indicating higher levels of depression. The change in PHQ-9 scores from baseline to one month, and from baseline to five months among by study arms will be reported.

d. Other outcomes.

- i. **Sustained health benefits:** To assess whether any improvements outcomes were sustained, researchers will evaluate the hospitalization and emergency department visits, four months after the intervention ended (at 9 months).

- 1. Admissions to Zuckerberg San Francisco General Hospital from baseline to 9 months, as determined by medical records. Number of admissions to Zuckerberg San Francisco General Hospital from baseline to 9 months, by study arm, adjusting for baseline values (-3 to 0 months).
- 2. Emergency room utilization at Zuckerberg San Francisco General Hospital from baseline to 9 months, as determined by medical records. Number of admissions to the emergency room at Zuckerberg San Francisco General Hospital from baseline to 9 months, by study arm, adjusting for baseline values (-3 to 0 months).

ii. Process outcomes 24)

23) **Analysis methods:**

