- a. **Preliminary/Descriptive analyses.** Frequency tables for all variables and measures of central tendency and variability for continuous variables will characterize the sample and be stratified by randomization arm to check for non-equivalence. If the two arms differ at baseline on any covariates, propensity scores approach will be used to obtain the desired marginal effect estimates under the counterfactual assumption of balanced arm.

25) Analysis methods to be used and how the treatment effects will be presented:

- a. Aim 1, Hypothesis 1. The intervention will lead to improved heart failure quality-of-life (primary outcome) and reduced acute care utilization (secondary outcomes) in the intervention arm compared to the control arm. Intent-to-treat analyses will assess whether the intervention will result in improved changes in primary and secondary outcomes with mixed effects models. These mixed models are equivalent to repeated measures models. Study arm (intervention or control), visits (baseline, month 1 and month 5), and the interactions between arms and visits will be the fixed effects and individuals will be considered as random effects.

Alternative analyses will be done using analysis of covariance in which the 5 month (and 1 month) outcome measures will be regressed on the corresponding baseline outcome measures and study arm. Analysis of covariance allows relaxing the assumption that the

baseline and follow-up measures have a 1:1 relationship and testing the assumption that the relationship between the baseline and follow-up measures are the same.

Additional analyses will be done to check robustness if the two arms differ at baseline by controlling for the propensity score or the covariates that were important in the propensity score.

For primary and secondary outcomes, Box-Cox transformations will be used to correct for skewness if needed.

To compare the probabilities of hospitalization and emergency room visits by study arm, a log-rank test will be performed, and visualized using Kaplan-Meier curves.

- b. Aim 2, Hypothesis, The intervention will improve food security, reduce healthcare utilization, and improve dietary behavior, that in turn will improve mental health (depressive symptoms), and medication adherence. Analysis for intermediate outcomes will be performed using mixed effects models, as described in Aim 1.
- c. Any planned sensitivity analyses for each outcome, where applicable: Not applicable.

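### Item 25a puts an arm-by-visit model of changes first for admission and ED counts, but items 22b.i and 22d.i define window counts adjusted for the prior 3-month count; ANCOVA fits that definition and should lead

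*Combined protocol and SAP*

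**What the plan says.** - **Lead analysis.** Section 6, item 25a names acute care utilisation as the secondary outcomes of Aim 1 and then states: "Intent-to-treat analyses will assess whether the intervention will result in improved changes in primary and secondary outcomes with mixed effects models". The model is specified as: "Study arm (intervention or control), visits (baseline, month 1 and month 5), and the interactions between arms and visits will be the fixed effects", with individuals as random effects. No distribution, link or residual structure is given.
- **Presentation.** Section 3, item 8 also works in changes, and names readmission: "differences between arms in changes in outcomes from baseline to 1 month to capture changes in acute heart failure symptoms and 30-day readmission".
- **Outcome definitions.** Items 22b.i.1 to 8 define eight counts. Each is a number of events over 0-1 or 0-5 months, for example "Number of admissions to any emergency room from baseline to 1 month, by study arm, adjusting for baseline values (-3 to 0 months", or "from baseline to 5 months, by study arm, adjusting for baseline values (-3 to 0 months". Items 22d.i.1 and 2 define two more: "from baseline to 9 months, by study arm, adjusting for baseline values (-3 to 0 months".
- **The model that matches the definitions.** Item 25a adds: "Alternative analyses will be done using analysis of covariance". It covers months 1 and 5, with the baseline measure as a covariate.
- **Skewness.** "For primary and secondary outcomes, Box-Cox transformations will be used to correct for skewness if needed".
- **Events as probabilities.** A log-rank test and Kaplan-Meier curves are planned. They address the probability of an event, not the counts.

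**The concern.** In an arm-by-visit model the pre-baseline count is a row of the outcome, not a covariate. The treatment estimate is the between-arm difference in (follow-up count minus prior count). That suits KCCQ, which is on the same 0-100 scale at every visit. For the utilisation counts the three rows span 3, 1 and 5 months, and the 1-month count is contained in the 5-month count.

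Item 25a itself says that ANCOVA relaxes an assumed 1:1 relationship between baseline and follow-up. For a 1-month count against a 3-month count, that assumption cannot hold at stable event rates. At stake are the precision of the 30-day readmission comparison, clarity on which estimate is reported for each count, and a stated model for the 9-month counts, which neither item 25a (visits to month 5) nor item 25b (intermediate outcomes) reaches.

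**Working it through.** **The plan's own figure.** The only sample size is for KCCQ: 2 x (1.96 + 0.842)^2 x (20/10)^2 = 62.8, so 63 per arm; 63/0.80 = 78.75, so 79 per arm and 158 in total. It reproduces. No event rate or power is given for the utilisation counts, so what follows rests on assumptions.

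**Inputs**
- From the documents: windows of 3 months before baseline and 1, 5 and 9 months after (items 22b.i, 22d.i); 79 and 82 participants after early withdrawals (item 20).
- Assumed: Poisson counts with a gamma frailty per person; rate r = 0.05-0.30 events per month; frailty variance v = 0.5-4; complete data; no cap on prior admissions. Write a = v x r, which runs from 0.025 to 1.2.

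**Linear model on raw counts.** Let the expected follow-up count be m x r. For month 1, m = 1, 2 or 3 (month-1 rate constant, doubled, tripled). For month 5, m = 5, 6 or 7 in the same scenarios. Per person, dividing by r:
- variance of the change: m + 3 + (m - 3)^2 a
- residual variance after ANCOVA: m[1 + (m + 3)a]/(1 + 3a)
- best coefficient on the prior count: m x a/(1 + 3a). For m = 1 this is always below 1/3; the change contrast fixes it at 1.

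The SE ratio (change/ANCOVA) is the square root of the variance ratio:

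| Contrast | Variance ratio | SE ratio, a = 0.025 | SE ratio, a = 1.2 | Range of SE ratio |
|---|---|---|---|---|
| Month 1, constant rate | 4(1+a)(1+3a)/(1+4a) | 2.00 | 2.64 | 2.00-2.64 |
| Month 1, rate doubled | (5+a)(1+3a)/(2+10a) | 1.55 | 1.43 | 1.40-1.55 |
| Month 1, rate tripled | 6(1+3a)/(3+18a) | 1.37 | 1.06 | 1.06-1.37 |
| Month 5, constant rate | (8+4a)(1+3a)/(5+40a) | 1.20 | 1.05 | 1.00-1.20 |

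With m = 6 or 7 included, the month-5 range is 1.00-1.21. Excluding people with six or more admissions in the prior 12 months (item 18) trims the prior admission counts. Modelled as at most 4 or at most 5 admissions besides the index one, the cap gives month-1 ratios for admissions of 1.70-1.99, 1.28-1.54 and 1.13-1.36. No such cap applies to ED visits.

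**Power, simulated.** At rate 0.15, frailty variance 1, constant rate and an assumed rate ratio of 0.6, month-1 power is 7.5% for the change contrast and 17.7% for ANCOVA with robust SE.

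**Log link instead.** On the log-rate scale, window length cancels from the arm contrast. A simulated within-person Poisson contrast was compared with Poisson regression on log(1 + prior count) with robust SE. The month-1 SE ratio was 0.96-1.21 over six rate/frailty pairs from 0.1/0.5 to 0.3/4, with the month-1 rate constant or doubled. At the example setting above, power was about 14-15% against 16-17%.

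**Single residual variance (conditional).** A linear random-intercept model with one residual variance gives both contrasts the same variance, (16 + 24a)/3. The true values at constant rates are 4 + 4a (month 1) and 8 + 4a (month 5). The month-1 SE is then 16-30% too large. The month-5 SE runs from 17% too small to 8% too large (type I error 10.5% down to 3.4%), crossing at a = 2/3. Visit-specific variances remove this error but not the precision loss.

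**Month 9.** Item 5 starts the controls' meals in the sixth month. With an assumed rate ratio of 0.6 while on food and none after, the expected 0-9 month ratio is (5 x 0.6 + 4)/(5 + 4 x 0.6) = 7/7.4 = 0.95. Against no programme it would be 7/9 = 0.78. If the effect persists after the food ends, the figures are 5.4/7.4 = 0.73 and 5.4/9 = 0.60.

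**The case against.** **The large ratios depend on an unstated linear model.** This stands. Item 25a says only mixed effects models. Linear is the likelier reading, because the companion analysis is ANCOVA and skewness is handled by Box-Cox, but a log-link model would remove most of the loss. The constant-rate figures are also the least apt scenario for patients enrolled at discharge after an exacerbation; an early peak in events shrinks the ratio.

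**The plan does rank its analyses.** This stands too. A reader might infer that the SAP leaves two equal lead estimates for each count. It does not: the mixed model comes first and ANCOVA is the alternative. The fault is that the first-ranked model does not match the definitions in item 22. One can reasonably let the outcome-specific wording of item 22 govern, but the text does not say so.

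**The 9-month counts are not wholly unplanned.** A reader might infer that they have no analysis. Item 22d.i does give the arm comparison and the adjustment variable; only the model form is missing.

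**Data limits.** The calculation assumes complete counts on 79 and 82 people. Item 16 limits ITT to those with a follow-up visit, the any-hospital counts need self-report, and month-5 retention was 60 and 59. The proposed ANCOVA has no person-time term. These limit the figures but do not favour the change model.

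**Conclusion.** The mismatch is real: item 25a's first-named model, and item 8's wording, do not estimate the utilisation outcomes as items 22b.i and 22d.i define them. The consequence is mainly lost precision at month 1, and only on the linear reading: an SE 2.0-2.6 times that of ANCOVA at constant rates, 1.4-1.55 times with a doubled and 1.06-1.37 times with a tripled month-1 rate, under the assumed rates and frailties without the cap. At month 5 the loss is small (1.00-1.21). With a log link it is small at month 1 as well.

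Two stronger readings are not supported. Unequal windows do not bias the arm contrast when arms are balanced, because the drift cancels between arms. If the 27 against 4 early withdrawals in item 19 left prior counts unbalanced, the two analyses could give different estimates, but the documents do not show such an imbalance. Nor does the plan imply wrong type I error in general: that arises only if one residual variance is fitted, which it does not state.

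Month-1 power is low under any method. These are secondary and other outcomes of a pilot, and the primary KCCQ analysis is untouched. The change is worth making because it is nearly free.

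**What to change.** - In item 25a, limit the arm-by-visit mixed model to KCCQ and the other repeated scale scores.
- For each utilisation count, make the planned ANCOVA the lead: one regression per window of the follow-up count on arm and the -3 to 0 month count, with robust SE. In simulations under no effect its type I error was 4.5-5.6%.
- If a rate ratio is wanted, give Poisson regression with robust SE and log(1 + baseline count) as supporting; its simulated type I error ranged more widely, 3.3-7.7%.
- Extend the same ANCOVA to the two 9-month counts. State that this contrast compares early with delayed programme, because controls start meals in the sixth month.
- Reword item 8 so that these counts are not presented as changes.
- If outcome data have already been examined, say so and report both analyses.

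The cost is a few sentences of SAP text and no new data. The downside is that month-1 estimates still rest on few events, and ANCOVA gives mean differences rather than rate ratios.

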- a. Participants were recruited through reviewing patient lists of hospitalizations in collaboration with providers in the Family Medicine and Cardiology Departments at San Francisco General Hospital. At provider meetings, research staff presented study details and eligibility guidelines.
- b. Screening was conducted in two stages, during an initial review of medical charts and at a visit with a participant while they were in the hospital prior to discharge. During the medical chart screening, potential participants were screened for congestive heart failure exacerbation diagnosis during their current hospital admission, age 18 years or older, language English or Spanish, less than 6 admissions to ZSFG in the last 12 months, no end stage renal disease diagnosis or known plan to initiate dialysis within 6 months, no severe aortic stenosis diagnosis, no mention of life expectancy less than 1 year, no cognitive impairment, currently housed, discharge plan for patient to discharge home, and currently living in San Francisco. Participants who met all criteria then proceeded to the in-hospital screening, which included confirming potential participants are housed and living in San Francisco, are not receiving more than 7 meal per week of food support, do not have any disqualifying allergies to commonly used foods used at POH, have a refrigerator and freezer to store food and are able to reheat and prepare meals and snacks at home, are able to eat by themselves or have assistance to eat, have cognitive capacity to consent to be in a research study, and are not moving in the next 6 months to a housing situation that does not meet study eligibility criteria.
- c. A summary will be provided indicating the number of participants screened, number of participants eligible, non-eligible and reason for non-eligibility, number of participants enrolled, number of participants eligible but not enrolled and reason, and number of participants randomized.

18) Eligibility – summary of eligibility criteria

Criteria for inclusion of subjects:

1. Adults hospitalized at ZSFG with acute decompensated heart failure/congestive heart failure exacerbation
2. Adults with their primary residence within San Francisco
3. Age: >18 years old
4. Languages: English or Spanish
5. Housed at a location where they would be able to securely receive, store and reheat food

Criteria for exclusion of subjects

1. Patients with severe or critical aortic stenosis.

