2. Patients with six or more hospital admissions within the last twelve months
3. Patients who are being discharged to a living facility that provides meals to residents.

4. Patients who anticipate moving from their current housing situation to one that does not meet our inclusion criteria within six months of enrollment.
5. Patients who are part of meal provision program that provides more than 7 meals a week to the patient.
6. Patients who are unable to feed themselves and do not have adequate support to help them with feeding.
7. Patients with limited physical, cognitive, or behavioral abilities that would interfere with their ability to follow-up with a study as determined by their ability to receive the Project Open Hand services and follow up with survey interviews
8. Patients with anticipated life expectancy of less than a year.
9. Patients who lack capacity to consent to a research study.
10. Patients currently requiring dialysis or determined to need dialysis in the next 6 months.
11. Patients with severe allergies to eggs, soy, wheat, nuts, seeds, seed oils, pineapple, raisins, or certain vegetables such as onions (allergies are considered on a case-by-case basis in consultation with Project Open Hand).

19) **Recruitment** – A CONSORT flow diagram will be used to summarize the number of participants who were:

- a. Assessed for eligibility at screening
 - i. Among people with heart failure, 2996 people were assessed for eligibility
 1. 2451 did not meet the inclusion criteria
 2. 127 Discharged before doing the baseline evaluations
 3. 226 were not interested in participating in the study
 - ii. Eligible and randomized
 1. 192 were eligible and randomized
 - a. 106 allocated in the intervention arm
 - i. 27 were early withdrawals
 - b. 86 allocated in the control arm
 - i. 4 were early withdrawals

See CONSORT diagram for detail on reasons for ineligibility

20) Withdrawal/follow-up

Reasons and details of withdrawal and lost to follow up at month 1 and 5 for both arms will be reported and summarized in the CONSORT flow diagram.

- a. Level of withdrawal, e.g., from intervention and/or from follow-up
 - i. Participants were withdrawn from the study due to unavailability to immediately reach out by phone, not meeting the eligibility criteria or deceased immediately following the randomization.

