Table 1: Baseline characteristics of CaRDS participants

Socio-demographic	Age, current gender, race/ethnicity, household size, relationship status, educational attainment
Economic welfare	Household food insecurity, sources of income, food support sources
Clinical	Heart failure quality of life; general health-related quality of life; medication inventory; blood pressure
Nutrition	Dietary quality; food consumption patterns
Mental Health	Depressive symptoms
Behavioral	Self-reported medication adherence; alcohol use, drug use
Healthcare utilization	Recent hospitalizations, ED visits, doctor visits

Section 6: Analysis

22) **Outcome definitions**

a. Aim 1: Primary Outcomes: Heart failure quality of life: The primary outcome for Aim 1 will be heart failure quality of life, which was assessed using the Kansas City Cardiomyopathy Questionnaire (KCCQ) at baseline, 1 month and 5 months, among all study participants. The Kansas City Cardiomyopathy Questionnaire is a 23-item instrument that quantifies physical function, symptoms (frequency, severity and recent change), social function, self-efficacy and knowledge, and quality of life. An overall summary score can be derived from the physical function, symptom (frequency and severity), social function and quality of life domains. A clinical summary score can be obtained from the symptom frequency and burden domains and the physical limitation domain. Scores are transformed to a range of 0-100, in which higher scores reflect better health status.

For analysis of the primary outcomes, we will compare:

- i. Change in the overall KCCQ scores from baseline to five months, by study arm.
- ii. Change in the overall KCCQ scores from baseline to one month, by study arm.
- iii. Change in the KCCQ clinical summary score from baseline to five months, by study arm,
- iv. Change in the KCCQ clinical summary score from baseline to one month, by study arm,
- v. Change in the overall physical domain KCCQ scores from baseline to five months, by study arm.
- vi. Change in the overall physical domain KCCQ scores from baseline to one month, by study arm.

b. Aim 1: Secondary outcomes:

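### The primary KCCQ model names only a person random effect, so its standard errors for change can be materially off if the three visits do not share a common variance and correlation; the SAP should name an unstructured covariance.

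*Combined protocol and SAP*

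**What the plan says.** Section 6, item 25a, gives the lead intention-to-treat analysis of the primary outcome as a mixed model over "visits (baseline, month 1 and month 5"), in which "the interactions between arms and visits will be the fixed effects and individuals will be considered as random effects". It adds: "These mixed models are equivalent to repeated measures models". It states no residual covariance structure, random slope, robust standard error or degrees-of-freedom method. Item 25b applies the same model to the Aim 2 outcomes, and item 25c lists no sensitivity analyses.

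Item 25a then adds a second approach: "Alternative analyses will be done using analysis of covariance in which the 5 month (and 1 month) outcome measures will be regressed" on the baseline value and arm.

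The KCCQ is "assessed using the Kansas City Cardiomyopathy Questionnaire (KCCQ) at baseline, 1 month and 5 months" (item 22a). The documents do not state outright where baseline was taken, but two places imply that it was in hospital. The second screening stage took place "at a visit with a participant while they were in the hospital prior to discharge" (item 17b), and the recruitment counts include "127 Discharged before doing the baseline evaluations" (item 19).

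The sample size (item 7) works directly from the SD of 5-month change, "assuming 80% power for a two-sided test at alpha of 0.05, and SD of 20.0".

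**The concern.** A random intercept with independent residuals implies compound symmetry: equal variance at every visit and equal correlation between every pair of visits. The model then estimates one residual variance from all within-person variation and uses it for every change contrast.

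There is reason to doubt that restriction here. Baseline appears to fall during an admission for an exacerbation, while months 1 and 5 follow discharge. Item 8 says the 1-month contrast is meant to capture change in acute symptoms. If the two follow-up scores resemble each other more than either resembles baseline, the smaller month-1-to-month-5 variation pulls the residual variance down, and the standard error for baseline-to-month-5 change comes out too small. Simple decay of correlation with time does the same at month 5. The opposite pattern makes the standard error too large.

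The p-value and confidence interval for the primary outcome are at stake.

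**Working it through.** **The plan's own figure.** With a difference of 10, SD of change 20, two-sided 0.05 and 80% power: n = 2 × (1.960 + 0.842)² × 20² / 10² = 62.8, so 63 per arm. Dividing by 0.80 retention gives 78.75, so 79 per arm and 158 in total. Both figures match item 7. The calculation uses the SD of change directly, so the covariance question does not alter it.

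**Complete-data formula.** For three visits and a random-intercept model:
- model variance of any change = mean of the three pairwise-difference variances;
- SE ratio (model / true) = √(that mean / true variance of the change tested);
- actual type I error = 2 × [1 − Φ(1.96 × ratio)].

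**Assumed inputs.** The documents give no visit SDs or correlations. With an SD of 20 at each visit, a difference variance is 800 × (1 − r). A correlation of 0.5 gives 400, which matches the plan's SD of change of 20. Correlations are listed as baseline–month 1 / baseline–month 5 / month 1–month 5.

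| Correlations | Difference variances | Mean | Month-5 SE ratio | Month-5 type I error |
|---|---|---|---|---|
| 0.5/0.5/0.5 | 400, 400, 400 | 400 | 1.000 | 5.0% |
| 0.5/0.5/0.8 | 400, 400, 160 | 320 | 0.894 | 8.0% |
| 0.4/0.3/0.7 | 480, 560, 240 | 426.7 | 0.873 | 8.7% |
| 0.5/0.3/0.5 | 400, 560, 400 | 453.3 | 0.900 | 7.8% |
| 0.6/0.6/0.3 | 320, 320, 560 | 400 | 1.118 | 2.8% |

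**With the trial's retention.** Item 20 gives 79, 75 and 60 intervention participants and 82, 78 and 59 control participants at baseline, month 1 and month 5. REML random-intercept fits to 4,000 simulated trials per scenario, with dropout completely at random, gave:

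| SDs | Correlations | Month-1 error | Month-5 error |
|---|---|---|---|
| 20/20/20 | 0.5/0.5/0.5 | 4.8% | 5.1% |
| 20/20/20 | 0.5/0.3/0.5 | 3.7% | 7.1% |
| 20/20/20 | 0.4/0.3/0.7 | 6.5% | 8.1% |
| 20/20/20 | 0.3/0.2/0.7 | 6.6% | 7.9% |
| 20/24/24 | 0.4/0.3/0.7 | 6.2% | 6.8% |
| 24/20/20 | 0.4/0.3/0.7 | 6.8% | 7.9% |
| 20/20/20 | 0.6/0.6/0.3 | 3.5% | 3.5% |
| 20/25/25 | all 0.5 | 4.0% | 4.9% |
| 25/20/20 | all 0.5 | 5.5% | 5.3% |

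At 0.4/0.3/0.7 with equal SDs, the mean model SE at month 5 was 3.64 against a true value of 4.06. Further runs with equal SDs gave month-5 errors of 6.1% (0.5/0.5/0.7), 6.3% (0.6/0.5/0.5), 6.4% (0.5/0.5/0.75) and 8.6% (0.6/0.5/0.8). The simulations keep the eight participants with baseline only, whom item 16a excludes; they add almost nothing to the estimates of change.

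**Alternatives.** The planned ANCOVA held its month-5 level at 4.5–5.6% in every scenario in the table. In a separate set of 3,000 trials per scenario, an unstructured covariance held 4.8–5.1%. Under true compound symmetry the mean month-5 SE was 3.50 with the random intercept and 3.52 with the unstructured covariance, a loss of about 0.3% before rounding.

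**The case against.** The strongest reply has four parts.

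- **The plan is silent rather than explicit.** A mixed model with unstructured residuals is also a repeated measures model, so the equivalence sentence rules nothing out. That is fair: the random intercept is the natural reading, not a stated choice. But silence leaves the structure to be picked after the data are seen, so it still needs fixing.
- **Failure of compound symmetry need not matter.** A reader might infer that the standard errors are wrong whenever it fails. They are not. With complete data, equal variances of the pairwise differences are enough. SDs of 18.7, 20.0 and 21.4 with correlations 0.47/0.51/0.54 break compound symmetry, yet all three difference variances equal 400 and the standard errors are exact. Unequal SDs alone did little in the simulations.
- **ANCOVA is already planned and does not need the assumption.** This stands, and it gives a pre-specified comparator. It is still labelled the alternative, and at month 5 it uses only the 60 + 59 = 119 of 161 participants with that score (74%), although item 16d declines complete-case analysis.
- **The trial is a pilot, and the direction of error is not fixed.** Also fair. The size is modest and can be conservative, which limits the weight of the point. It does not argue against so cheap a change.

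**Conclusion.** The point holds as a conditional one. On its natural reading, the primary model imposes a restriction that the design gives reason to doubt, with no robust standard error behind it. With the trial's retention, month-5 type I error is about 6–9% if the follow-ups correlate more with each other than with baseline or if correlation decays with time, about 5% under compound symmetry, and about 3–4% in the reverse pattern. Month-1 error ranges from about 3.5% to 7%. All of this rests on assumed SDs and correlations, on dropout completely at random, and on an in-hospital baseline that is inferred.

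Two stronger readings are not supported. One is that the trial's nominal 5% level and 95% coverage are in fact lost: without visit SDs or correlations, the documents cannot show that. The other is that every Aim 2 outcome is affected in the same way. The food frequency and medication adherence items ask about the preceding month, so the argument from an acute in-hospital baseline does not carry over to them.

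This is a cheap improvement, not a defect that invalidates the primary analysis.

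**What to change.** In item 25a, specify REML with an unstructured 3×3 covariance across baseline, month 1 and month 5, and small-sample degrees of freedom. If that does not converge, fall back on the random intercept with cluster-robust standard errors by person. Replace the sentence on equivalence with the named structure. Use the same specification where item 25b applies this model to continuous Aim 2 outcomes.

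The cost is a short SAP edit and one model option: six covariance parameters instead of two, from 79 + 75 + 60 + 82 + 78 + 59 = 433 person-visits. If compound symmetry does hold, the precision loss is about 0.3%. The sample size stays as it is.
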